3.1.2 Rationale for Treatment with Atezolizumab

Encouraging clinical data emerging in the field of tumor immunotherapy has demonstrated that therapies focused on enhancing T-cell responses against cancer can result in significant clinical benefit to patients across a broad array of advanced malignancies (Hodi et al., 2010; Kantoff et al., 2010). The PD-L1 pathway serves as an immune checkpoint to dampen immune responses in states of chronic antigen stimulation, such as chronic infection or cancer. PD-L1 is an extracellular protein that downregulates immune responses through binding to its two receptors, PD-1 and B7-1. PD-1 is an inhibitory receptor expressed on T cells following T-cell activation; expression is sustained in states of chronic stimulation (Blank, Gajewski, & Mackensen, 2005; Keir, Butte, Freeman, & Sharpe, 2008). B7-1 is a molecule expressed on antigen-presenting cells and activated T cells. Binding of PD-L1 to PD-1 and B7-1 inhibits T-cell proliferation and activation, cytokine production, and cytolytic activity, leading to the functional inactivation or exhaustion of T cells (Butte, Keir, Phamduy, Sharpe, & Freeman, 2007; J. Yang et al., 2011). Overexpression of PD-L1 on tumor cells may impede anti-tumor immunity, resulting in immune evasion (Blank & Mackensen, 2007). Therefore, interrupting the PD-L1 pathway is an attractive strategy for restoring tumor-specific T-cell immunity.

Targeting the PD-L1 pathway with atezolizumab has demonstrated activity in patients with advanced malignancies who have failed standard-of-care therapies. Objective responses have been observed across a broad range of malignancies, including non-small cell lung cancer (NSCLC), urothelial carcinoma, renal cell carcinoma (RCC), melanoma, colorectal cancer, head and neck cancer, gastric cancer, breast cancer, and sarcoma (see most current version of Atezolizumab Investigator's Brochure for detailed efficacy results). Atezolizumab has been generally well tolerated. Adverse events with potentially immune-related causes consistent with an immunotherapeutic agent, including rash, influenza-like illness, endocrinopathies, hepatitis or transaminitis, pneumonitis, colitis, and myasthenia gravis, have been observed (see most current version of Atezolizumab Investigator's Brochure for detailed safety results).

3.1.3 Pharmacology of Atezolizumab

Atezolizumab is a humanized antibody containing heavy chain VHIII and light chain Vkl subgroup sequences. The antibody lacks the N-linked oligosaccharides due to an asparagine to alanine substitution at position 298 of each heavy chain, resulting in a non-glycosylated antibody.

Atezolizumab is produced in Chinese hamster ovary (CHO) cells and is provided in 2-mL (Formulation F01 or early Phase I/II material) and 20-mL (Formulation F03 or late Phase I/II and Phase III material) glass vials. The diluent used with Formulation F01 is provided in 50-mL glass vials. The respective protein concentrations for Formulations F01 and F03 are 125 mg/mL and 60

Columbia University Irving Medical Center
Herbert Irving Comprehensive Cancer Center
AAAS4165_Version Date: 07/07/2021

mg/mL, respectively. Atezolizumab (F01 and F03) and diluent are in a solution containing histidine acetate, sucrose, and polysorbate 20.

3.1.4 Clinical Data to Date: Atezolizumab

For most up to date information on clinical data available, refer to current version of Institutional Brochure.

3.1.4.1 Effect of Atezolizumab in Humans

As of the August 2018 Investigator's Brochure (version 13), clinical data on atezolizumab as a single agent or in combination with chemotherapy or targeted agents are available from more than 20 studies. Atezolizumab is approved in the United States for the treatment of patients with locally advanced or metastatic urothelial carcinoma who fit the following criteria: 1) are not eligible for cisplatin-containing chemotherapy and whose tumors express PD-L1 (PD-L1 stained tumor-infiltrating immune cells covering $\geq 5\%$ of the tumor area), as determined by a US Food and Drug Administration (FDA)-approved test; or 2) are not eligible for any platinum-containing chemotherapy, regardless of PD-L1 status; or 3) have disease progression during or following any platinum-containing chemotherapy, or within 12 months of neoadjuvant or adjuvant chemotherapy. Atezolizumab is also approved for the treatment of previously treated locally advanced or metastatic non-small cell lung cancer (NSCLC).

Pharmacokinetic, exposure-safety, and exposure-efficacy data analysis, as reported in the Atezolizumab Investigator's (version 13) identified that age, body weight, gender, albumin levels, tumor burden, renal impairment, mild hepatic impairment, level of PD-L1 expression, or Eastern Cooperative Oncology Group (ECOG) status had no clinically relevant effect. Positive anti-drug antibody (ADA) status against atezolizumab led to approximately 13% reduction in overall exposure. The effect of hepatic impairment (bilirubin or aspartate aminotransferase $>$ upper limit of normal) on the pharmacokinetics of atezolizumab is unknown.

3.1.4.2 Effect of atezolizumab in combination with cobimetinib

The randomized phase 3 IMblaze370 study tested combination atezolizumab and cobimetinib versus atezolizumab or regorafenib alone in patients with advanced colorectal cancer who had progressed on or were intolerant of two lines of therapy. Of those treated with atezolizumab and cobimetinib, 61% experienced Grade 3/4 adverse events compared to 58% who were treated with regorafenib, an approved drug for metastatic colorectal adenocarcinoma. Diarrhea (11%), anemia (6%), increased blood creatine phosphokinase (7%), and fatigue (4%) were the most commonly observed all-cause Grade 3 – 4 toxicities in subjects treated with cobimetinib and atezolizumab (SAEs were reported in 40% subjects receiving combination therapy). Of the AEs, 26% of subjects experienced serious treatment-related AEs, 21% stopped treatment, and 61% required dose interruption or modification (Eng et al., 2019).

3.1.5 Tolerability profile during combination treatment

In studies investigating the combination of atezolizumab with other anti-cancer agents, the incidence of AEs in the treatment arms with combined use was consistent with the known safety profiles of the individual study drugs. Fatigue, decreased appetite, nausea and cough were adverse events reported in more than 10% of patients treated with atezolizumab monotherapy and in combination therapy. Through appropriate routine evaluations, investigational workup, and early mitigations, such as management guidelines, the majority of patients were able to continue atezolizumab therapy (see most current version of Atezolizumab Investigator's Brochure for detailed safety results).

3.2 Cobimetinib

3.2.1 Background

Cobimetinib is a potent and highly selective small molecule inhibitor for MEK1 and MEK2, which are known key players of the RAS/RAF pathway (see Section 2.0). Inhibition of MEK1 and MEK2 results in inhibition of ERK1/2 phosphorylation and thus decreased cell proliferation. Cobimetinib is a substrate of CYP3A4 and UGT2B7 and an inhibitor of isozymes CYP2D6 and CYP3A4. Cobimetinib accumulates in tumor xenografts and remains at high concentrations in the tumor after plasma concentrations have declined.

The inhibition of ERK1 phosphorylation by cobimetinib correlates more closely with concentrations of cobimetinib in tumor tissues than in plasma; in general, there is a good correlation between reduced ERK1 phosphorylation and efficacy in tumor xenograft models.

Nonclinical and *in vitro* metabolic profiling studies suggest that cobimetinib is a substrate for CYP3A4 and UGT2B7-mediated metabolism in human liver microsomes and recombinant enzymes; cobimetinib is an inhibitor of isozymes CYP2D6 and CYP3A4 *in vitro*. Cobimetinib is approximately 95% bound to human plasma proteins. The pharmacokinetics of cobimetinib has been characterized in multiple species, including mice, rats, dogs, and monkeys.

3.2.2 Toxicology

The nonclinical toxicity of cobimetinib was characterized in single-dose and repeat-dose studies in rats and dogs, a repeat-dose toxicity study in juvenile rats, reproductive and developmental studies in rats, genotoxicity studies (including *in vitro* bacterial and mammalian genotoxicity bioassays and *in vivo* micronucleus assays) in rats, and *in vitro* (3T3 mouse fibroblasts) and *in vivo* (pigmented rats) phototoxicity studies. The nonclinical safety assessment for cobimetinib identified degenerative effects in multiple tissues that are clinically manageable, and the potential for reproductive toxicity at therapeutically relevant exposures. It was not phototoxic or genotoxic *in vitro* or *in vivo*. When considered together with the clinical safety database and the intended treatment population, the results of the nonclinical toxicity program provide a safety profile that supports the use of cobimetinib in the treatment of cancers.

3.2.3 Clinical Data

Cobimetinib has been approved in the United States for the treatment of advanced melanoma in tumors that encode a mutation in *BRAF* V600E or V600K in combination with vemurafenib. Cobimetinib is generally well tolerated, but common AEs include fatigue, rash, diarrhea, nausea, emesis, edema, ophthalmological disorders, and abdominal pain. For the most up to date information on clinical data, refer to current version of Institutional Brochure. Clinical information regarding combination cobimetinib and hydroxychloroquine is listed above (Section 2.2).

3.3 Hydroxychloroquine

3.3.1 Background

Hydroxychloroquine sulfate is a colorless crystalline solid, soluble in water to at least 20%. Chemically, the drug is 2-[[4-[(7-Chloro-4-quinolyl)amino]penty]ethylamino] ethanol sulfate (1:1). The drug possesses antimalarial actions and also exerts a beneficial effect in lupus erythematosus (chronic discoid or systemic) and acute or chronic rheumatoid arthritis. The precise mechanism of action is not known. It is indicated for the suppressive treatment and treatment of acute attacks of malaria due to *Plasmodium vivax*, *P. malariae*, *P. ovale*, and susceptible strains of *P. falciparum*. It is also indicated for the treatment of discoid and systemic lupus erythematosus, and rheumatoid arthritis. The detailed mechanism by which hydroxychloroquine inhibits autophagy is currently unknown.

3.3.2 Clinical Data to Date

Hydroxychloroquine sulfate (HCQ) is supplied in 200mg tablets, and when supplied to healthy males resulted in peak blood concentration of 129.6ng/mL in 3.26 hours. The half-life of HCQ is 2963 hours (123.5 days). Renal clearance after 6 months of chronic exposure did not appear to change renal clearance. Dose adjust is not required for patients with renal impairment. In patients with rheumatoid arthritis (RA) there was large variability in the absorption of the drug.

3.3.3 Contraindications

Hydroxychloroquine is contraindicated in patients with known hypersensitivity to 4-aminoquinoline compounds.

Adverse events noted from hydroxychloroquine include:

Ocular -

Irreversible retinal damage has been observed in some patients who have received hydroxychloroquine. Risk of this AE increases with dosage greater than 6.5mg/kg of actual body weight, use of durations greater than five years, subnormal glomerular filtration, use of some concomitant drug products, such as tamoxifen citrate, and concurrent macular disease.

Cardiotoxicity and QT Prolongation –

Columbia University Irving Medical Center
Herbert Irving Comprehensive Cancer Center
AAAS4165_Version Date: 07/07/2021

Postmarketing cases of lifethreatening and fatal cardiomyopathy have been reported. Patients may present with atrioventricular block, pulmonary hypertension, sick sinus syndrome, or cardiac complications. ECG findings may include atrioventricular right or left bundle branch block.

Worsening of psoriasis and porphyria –

Use of hydroxychloroquine in patients with this condition may precipitate a severe attack.

Proximal Myopathy and Neuropathy –

Progressive muscle weakness and proximal muscle group atrophy have been reported, including depressed tendon reflexes and abnormal nerve conduction.

Neuropsychiatric events, including suicidality –

Suicidal behavior has been rarely reported in patients treated with hydroxychloroquine.

Hypoglycemia –

Hydroxychloroquine has been reported to cause severe hypoglycemia, including loss of consciousness, which can be life threatening in patients who may or may not be on anti-diabetic therapy.

Other –

Hydroxychloroquine should be used in caution with patients who have compromised hepatic or renal function. Blood counts should be monitored to ensure no myelosuppression. Dermatitis has been reported with the use of hydroxychloroquine.

Drug Interactions –

Digoxin, insulin or other antidiabetics, drugs that prolong QT interval, antiepileptics, methotrexate, cyclosporine, praziquantel, antacids, cimetidine, and ampicillin have significant interactions with hydroxychloroquine.

3.4 Other Agent(s)

N/A

4. STUDY DESIGN

4.1 General Design

4.1.1 Phase 1

The objective of this study is to determine the maximum tolerated dose (MTD) of the combination of cobimetinib, atezolizumab, and hydroxychloroquine. We will evaluate three dose combinations. Patients will be treated with combination therapy at the designated dose levels depicted in Table 1, based on a 28 day cycle (Section 7.3). The MTD is defined as the dose associated with a target probability of dose limiting toxicity of 0.30. The primary endpoint is DLT in the first cycle of treatment.

Columbia University Irving Medical Center
Herbert Irving Comprehensive Cancer Center
AAAS4165_Version Date: 07/07/2021

Given that cobimetinib is approved at a dose of 60 mg orally daily and hydroxychloroquine was well tolerated at 600 mg orally twice daily, we feel that the combination will be well tolerated (Wolpin et al., 2014). Cobimetinib and atezolizumab were tested in advanced colorectal cancer in IMblaze370, a large randomized phase 3 clinical trial (Eng et al., 2019) with proportion of patients experiencing grade 3 and over adverse events similar to those who received the FDA approved Regorafenib. Subjects will receive cobimetinib in cohort 1 and 2 at a lower dose (40mg oral daily) compared to that tested in IMblaze370 (60mg oral daily). Given that, other than ocular and hepatic toxicity, hydroxychloroquine has little to no overlapping adverse events with cobimetinib and atezolizumab, we do not anticipate significant toxicities with this combination at the doses being tested. Ocular toxicities with hydroxychloroquine are observed at high cumulative doses and will be monitored by required scheduled ophthalmological evaluations throughout the study period. We will initiate Phase 1 at dose level 1 using a combined 3+4 and time-to-event continual reassessment method (TITE-CRM). Table 1. Cohort dose levels.

| Patient No. | Dose Level | Hydroxychloroquine (mg) (oral; 1200mg/day; Days 1-28) | Cobimetinib (mg) (oral; 40-60mg/day; Days 1-21) | Atezolizumab (mg) (IV; 840mg every two weeks) |
|------------------|------------|---|---|---|
| 1, 2, 3 | 1 | 600mg twice per day | 40mg | |
| 4, 5, 6 | 2 | 600mg twice per day | 40mg | 840mg |
| 7, 8, 9 10-18 | 3 | 600mg twice per day TITE-CRM | 60mg | 840mg |

Phase I Statistical Considerations

The MTD will be estimated using a two-stage time to event continual reassessment method (TITE-CRM), whereby in the first stage patients will be assigned to 3-patient cohorts (see table below) in the absence of DLT. However, once a DLT is observed, we will initiate the second stage and patients will be assigned using the TITE-CRM. The initial design for the two stage was obtained using the method by Jia, et al (Jia, Ivanova, & Lee, 2017).

Table 2. Selection probabilities and average expected number of patients assigned to each dose based on the two stage TITE-CRM (N=18)

| Doses Level | | 1 | 2 | 3 |
|-------------|-------------------------|-----|-----|-----|
| Scenario 1 | DLT rate | 30% | 45% | 55% |
| | P(Selection) | 74% | 23% | 4% |
| | Average Number Assigned | 11 | 4 | 3 |

Columbia University Irving Medical Center
Herbert Irving Comprehensive Cancer Center
AAAS4165_Version Date: 07/07/2021

The advantage of the TITE-CRM is that it uses the patient's partial information before a complete follow-up is achieved. As a result, we can conduct the trial in a continuous fashion without having patients be turned away due to waiting time. The TITE-CRM will use an empirical dose-toxicity model, with a sample size

| | DLT rate | 15% | 30% | 45% |
|-------------------|--------------------------------|-----|-----|-----|
| Scenario 2 | P(Selection) | 24% | 53% | 23% |
| | Average Number Assigned | 6 | 6 | 6 |
| Scenario 3 | DLT rate | 5% | 15% | 30% |
| | P(Selection) | 1% | 25% | 74% |
| | Average Number Assigned | 2 | 5 | 11 |

of 18. The prior distribution of the model parameter is assumed to be normal with a mean of 0 and a variance of 1.34. The dose-toxicity model is calibrated such that the eventual dose yields between 18% and 32% DLT (Cheung & Chappell, 2002; Lee & Ying Kuen, 2009) and good operating characteristics across a wide range of potential scenarios of toxicity profiles. Given that the majority of the toxicities for the cobimetinib and atezolizumab trial occurred in the first cycle of treatment, the proposed toxicity evaluation period is 4 weeks. In the first stage, each cohort will be followed for the entire 4 weeks in the absence of a DLT. Once a DLT is observed, we will impose a minimum of 1 week of observation between patients in the second stage of the design. We do not allow for dose skipping during dose escalation or escalation immediately after a dose limiting toxicity. **Patients who do not complete 80% of dosing due to reasons other than treatment-related toxicity (e.g. non-compliance) will need to be replaced. Moreover, patients who discontinue due to reasons other than treatment-related toxicity (i.e. progression or death) prior to completing 4 weeks of therapy without having experienced a DLT will be considered not evaluable and be replaced.** Partial toxicity information from subjects that are greater than 80% compliant may be included for dose assignments and will continue to be used for future dose assignments unless the patient is not evaluable and/or discontinues prior to the 4 week DLT evaluation. To evaluate the performance of the method, 2000 simulations under these scenarios of toxicity profiles were done. The operating characteristics of our design under these scenarios are displayed in Table 2. Based on these simulation results, the 18-patient design selects the correct MTD with probabilities over 53% under all possible scenarios. These simulations assume that the patients arrive at a rate of 4 patients every 4 weeks (i.e., a patient every week) which is our full toxicity evaluation window, and that a DLT occurs randomly and uniformly

Columbia University Irving Medical Center
Herbert Irving Comprehensive Cancer Center
AAAS4165_Version Date: 07/07/2021

within the observation window. Moreover, based on the various simulation scenarios, we expect

[figure not shown]

Figure 5. Simulated trial using time-to-event continuous reassessment method.

Each number represents an enrolled patient. Circled numbers depict time at which toxicity was experienced by that patient.

between 6 and 11 of the 18 patients will be assigned the MTD.

To illustrate the method using an example, Figure 5 displays a simulation of a sample design using the method based on scenario 2 (see Table 2), where the true MTD is dose level 2. In this simulated example, the recommended dose level is 2. The first three patients are assigned to dose level 1 in weeks 1, 2, and 3. By week 4 patient 1 has a DLT and we initiate the TITE-CRM with patients 4, 5, 6, and 7 being assigned dose level 1. With no DLTs, at week 7 the dose is escalated and patients 8, 9, 10 and 11 are assigned to dose level 2. With no DLTs, by week 12 the dose is escalated again and patient 12 is assigned to dose level 3. Patient 12 has a DLT and the dose is de-escalated with patient 13 to 18 being assigned to dose level 2, with two DLTs being observed among them. The estimated MTD is dose level 2 with an estimated probability of DLT of 0.27 and 90% probability interval of (0.12, 0.44). Two of the 10 patients assigned to dose level 2 have DLTs. With an accrual rate of 4 patients per month, this study takes a total of less than 6 months to complete.

4.1.1.1 Dose Limiting Toxicities for Phase 1

All patients who receive at least one dose of cobimetinib and hydroxychloroquine, with or without atezolizumab, will be evaluable for toxicity.

In order for a patient to be evaluable for DLT assessments, the patient must either incur a DLT during the DLT evaluation period, or have received at least 80% of the planned doses of hydroxychloroquine, cobimetinib, and if applicable, atezolizumab. Patients who do not fulfill one of these criteria should be considered non-evaluable for DLT assessment purposes, and be replaced.

A DLT is defined as an AE that is possibly, probably, or definitely related to study drug administration, and that is:

- Not due to the underlying malignancy;
- Has no clear evidence of an alternative etiology; and
- Meets one of the following CTCAE v.5.0 criteria during the first 28 days of hydroxychloroquine, cobimetinib, and if applicable, atezolizumab administration:
 - Any Grade ≥ 4 hematologic toxicity, except grade 4 lymphopenia, lasting ≥ 7 consecutive days
 - Grade 3 neutropenia with fever
 - Grade 3 thrombocytopenia with clinically significant bleeding
 - Any circumstance that results in dose reduction
 - Any Grade ≥ 3 non-hematologic toxicity except:
 - Nausea, vomiting, and/or diarrhea of Grade 3 severity that resolves within 7 consecutive days with optimal prophylaxis and/or treatment;
 - Grade 3 fatigue that resolves to Grade ≤ 2 within 7 consecutive days;
 - Grade ≥ 3 alkaline phosphatase that is related to underlying malignancy (eg, bone metastasis).
 - Grade ≥ 3 asymptomatic or mildly symptomatic rash will not be considered a DLT if the event can be adequately managed with supportive care, the event resolves to become asymptomatic and/or Grade ≤ 2 within 7 days, or the event continues for longer than 7 days in a patient who has not received appropriate supportive therapy.
 - Grade ≥ 3 elevation of serum creatine phosphokinase (CPK) level will not be considered a DLT if the event is asymptomatic (i.e., not accompanied by signs, symptoms, or other laboratory abnormalities associated with rhabdomyolysis or myocardial injury) and is deemed by the investigator to be clinically insignificant.
 - Grade 3 arthralgia will not be considered a DLT if the event can be adequately managed with supportive care or the event resolves to Grade ≤ 2 within 7 days.
 - Grade 3 fever (in the absence of any clinically significant source of fever) will not be considered a DLT if the event resolves to Grade ≤ 2 within 7 days or the event continues for longer than 7 days in a patient who has not received appropriate supportive care.

- Grade 3 laboratory abnormality will not be considered a DLT if the event is asymptomatic and is deemed by the investigator to be clinically insignificant.
- Grade 3 autoimmune thyroiditis or other endocrine abnormality will not be considered a DLT if the event can be managed by endocrine therapy that would not necessitate initiation of systemic corticosteroids.
- Grade ≥ 3 total bilirubin that is not attributed to disease progression
- Grade ≥ 3 AST or ALT, but not isolated elevation in ALT (non-specific) in subjects without metastatic disease in the liver
- AST or ALT $\geq 10X$ ULN in subjects with liver metastasis
- QTc interval ≥ 501 ms confirmed by a repeat ECG
- Grade ≥ 3 Creatine Kinase with symptoms of myalgia
- Grade ≥ 2 retinal events lasting greater than 14 days or Grade ≥ 3 retinal events that are confirmed by ophthalmologic examination
- Grade ≥ 3 rash that persists despite optimal treatment, and that does not resolve to Grade ≤ 2 within 7 days.

Final decisions on determination of DLTs will be made in consultation with the Principal Investigator. The Principal Investigator may decide not to further dose escalate based on clinical judgement.

DLTs are considered AEs of special interest, and require close monitoring and rapid communication with the Principal Investigator. A DLT may be serious or nonserious. The rapid reporting of DLTs allows ongoing surveillance of these events in order to prevent enrollment of subjects at inappropriate dose levels, therefore, DLTs will be required to be reported to the study email [contact] **within 24 hours** to the lead site by memo signed by the Affiliate Site PI/Treating Investigator. DLTs should also be reported in Velos. Please refer to Section 14.2 for Data Reporting Guidelines.

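### Table 2's average allocation does not match the two-stage TITE-CRM it is labelled with; Scenario 3 prints 2 patients at level 1, where the written rule gives at least 2.95

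*Combined protocol and SAP*

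**What the plan says.** Section 4.1.1 describes a two-stage design for 18 patients. For stage 1, "in the first stage patients will be assigned to 3-patient cohorts (see table below) in the absence of DLT"; TITE-CRM assignment begins once a DLT is observed. Table 1 places the first cohort at level 1 ("1, 2, 3 | 1 | 600mg twice per day | 40mg"). Each stage 1 cohort is followed for the full 4 weeks if no DLT occurs. The escalation limits are: "We do not allow for dose skipping during dose escalation or escalation immediately after a dose limiting toxicity". The worked example starts the same way: "The first three patients are assigned to dose level 1 in weeks 1, 2, and 3".

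Table 2 is captioned as giving selection probabilities and the "average expected number of patients assigned to each dose based on the two stage TITE-CRM (N=18"). The simulation results are presented as those of this design: "The operating characteristics of our design under these scenarios are displayed in Table 2". The Scenario 1 row reads "Average Number Assigned | 11 | 4 | 3"; Scenario 2 is printed as 6/6/6 and Scenario 3 as 2/5/11. The text then says that, across scenarios, "between 6 and 11 of the 18 patients will be assigned the MTD".

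**The concern.** A design that starts with three patients at level 1 should almost never treat fewer than three there, least of all when the level 1 DLT rate is 5%. A printed mean of 2 therefore suggests that the simulated design was not the written one.

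These rows, and the sentence drawn from them, are where the protocol tells its scientific and ethics reviewers how many patients each level is expected to treat. If they come from a different first-stage rule, the stated exposure by level is not that of the trial to be run. The other operating characteristics in the table then rest on an unconfirmed design as well.

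**Working it through.** **Step 1. Exact bound for Scenario 3, level 1 (no skeleton needed).**

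Inputs: start at level 1, 3-patient cohorts, no escalation straight after a DLT (section 4.1.1); DLT rate 5% at level 1 (Table 2).

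- Patient 1 has no DLT (probability 0.95). Patients 2 and 3 are then both at level 1: either no DLT has been seen when patient 3 enters, or patient 2's DLT has just been seen and bars escalation. Contribution: 3 patients.
- Patient 1 has a DLT (probability 0.05). Patient 2 is still at level 1, for the same reasons. Contribution: at least 2.

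Mean ≥ 0.95 × 3 + 0.05 × 2 = **2.95**.

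Weaker readings do not rescue the printed 2:

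- Ignoring the bar on escalation: 0.9025 × 3 + 0.0475 × 2 + 0.05 × 1 = 2.85.
- Counting only patient 1 whenever any of the first three has a DLT: 3 × 0.857 + 0.143 × 1 = 2.71, where 0.857 = 0.95³.

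None of these rounds to 2. Truncation is not the explanation either, because the printed row sums to 2 + 5 + 11 = 18.

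**Step 2. Choosing a skeleton from the worked example.**

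The protocol gives the empiric model and a normal prior with mean 0 and variance 1.34, but no skeleton. The worked example has DLTs in 1/7, 2/10 and 1/1 patients at levels 1, 2 and 3, and reports 0.27 (0.12, 0.44) at level 2. With pᵢ = sᵢ^exp(β), level 2 evaluated at the posterior mean of β, and a 90% interval from the mean ± 1.645 posterior SD:

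| Skeleton | Level 2 estimate (90% interval) |
|---|---|
| 0.169 / 0.30 / 0.443 | 0.268 (0.119, 0.444) |
| 0.124 / 0.25 / 0.398 | 0.267 (0.118, 0.442) |

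Both reproduce the protocol's figures. With weekly entry, both also reproduce the dose path of patients 4 to 13.

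**Step 3. Simulating the written design.**

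Settings: target 0.30, linear weights, one patient per week, DLT times uniform over 4 weeks, full stage 1 follow-up, no skipping, no escalation when a DLT was seen since the last assignment. First skeleton, 10,000 trials per scenario; Monte Carlo error about 0.05 patients.

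| | Printed allocation | Written design | Printed selection % | Written design % |
|---|---|---|---|---|
| Scenario 1 (30/45/55%) | 11 / 4 / 3 | 13.1 / 4.0 / 1.0 | 74 / 23 / 4 | 72 / 25 / 3 |
| Scenario 2 (15/30/45%) | 6 / 6 / 6 | 7.5 / 6.9 / 3.6 | 24 / 53 / 23 | 20 / 54 / 26 |
| Scenario 3 (5/15/30%) | 2 / 5 / 11 | 3.9 / 5.5 / 8.6 | 1 / 25 / 74 | 1 / 20 / 79 |

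Every simulated trial had at least 3 patients at level 1. As a plausibility check on Scenario 1, stage 1 reaches level 3 only if six patients have no DLT: 0.70³ × 0.55³ = 5.7%.

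**Step 4. Sensitivity (allocation in Scenarios 1; 2; 3).**

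- Second skeleton: 13.0/4.1/1.0; 7.4/7.0/3.7; 3.9/5.5/8.6.
- First skeleton, no 4-week wait in stage 1: 12.7/4.1/1.1; 7.2/6.8/3.9; 3.9/5.4/8.7.
- First skeleton, 1.34 read as the prior SD: 13.1/3.9/1.0; 7.5/6.7/3.8; 4.0/5.4/8.6.
- A grid of skeletons in steps of 0.02: 125 match 0.27 (0.12, 0.44), and 120 of them were simulated (1,000 trials per cell). Five cells miss the printed value every time:

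| Cell | Printed | Range over 120 skeletons |
|---|---|---|
| Scenario 1, level 1 | 11 | 12.5–14.3 |
| Scenario 1, level 3 | 3 | 0.3–1.3 |
| Scenario 2, level 3 | 6 | 1.8–5.1 |
| Scenario 3, level 1 | 2 | 3.7–4.5 |
| Scenario 3, level 3 | 11 | 5.0–9.4 |

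Fourteen of the 125 also match the example's dose path. In each of those, the worst cell is 2.3 to 3.3 patients from the printed value.

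**Step 5. Patients at the true MTD.** With the first skeleton the means are about 13.1, 6.9 and 8.6 in Scenarios 1, 2 and 3. Only Scenario 1 falls clearly outside 6 to 11.

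**The case against.** The strongest reply has four parts.

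- **The two-stage label may be right.** A two-stage TITE-CRM with single-patient first-stage steps and no 4-week wait gives 11.2/3.9/2.8, 6.0/6.2/5.8 and 2.5/4.6/10.9 with the first skeleton, within about half a patient of every printed cell. A one-stage TITE-CRM does about as well (11.0/4.1/2.8, 6.0/6.3/5.7, 2.3/4.7/11.0), though that match depends on the skeleton. This stands: the conflict is with the stated 3-patient, fully followed first stage, and the documents do not show what was simulated. It does not rescue the table, because neither alternative is the design in the text.
- **Only one of nine cells is disproved by arithmetic.** This stands. The rest is simulation with skeletons fitted to one illustrative trial whose figure is not available here, so its exact entry and DLT times are partly assumed. The protocol's 18% to 32% calibration range is also centred on 0.25, while the first skeleton is centred on 0.30. The second skeleton, centred on 0.25, gives nearly the same allocation.
- **The selection rows are not shown to be wrong.** This stands. They would be regenerated in a re-run, but that is not evidence against them.
- **The consequence is mild.** The table overstates exposure at level 3, and nothing operational depends on these rows. This limits the weight of the point but does not make the stated figures correct.

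**Conclusion.** The point holds. The Scenario 3, level 1 entry cannot come from the design as written: it is printed as 2 and must be at least 2.95, or 2.71 on the loosest reading. That result needs only the cohort rule and the 5% DLT rate.

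The wider mismatch depends on the simulation settings and on skeletons consistent with the worked example. On that basis Table 2 understates level 1 in Scenarios 1 and 3, by about 2 patients each. It overstates level 3 in all three scenarios, by about 2.0, 2.4 and 2.4 patients. Scenario 2, level 1 is too close to call, and the level 2 cells are not disputed.

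The protocol should correct this, but it is a fault in the reported operating characteristics and not in the conduct of the trial. That a different first-stage rule was simulated is a plausible inference only.

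**What to change.** 1. Confirm from the simulation code which first-stage rule was run: cohort size, follow-up between cohorts, and one or two stages.
2. If the written 3-patient first stage stands, re-run all of Table 2 under it and state the skeleton. Then restate the sentence on how many patients receive the MTD from the new output.
3. If another design is the intended one, reconcile the table's label with Table 1, the design text, the worked example and section 10.1.3. Section 4.1.1 calls the first part 3+4 and section 10.1.3 calls it 3+3, so the name should be made consistent at the same time.

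The cost of step 2 is one simulation run, one table and one sentence, with no change to dose assignment, sample size or conduct. Step 3 is a text reconciliation.
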